7.0 TRIAL PROCEDURES

7.1 **Trial Procedures**

The Trial Flow Chart - Section 6.0 summarizes the trial procedures to be performed at each visit. Individual trial procedures are described in detail below. It may be necessary to perform these procedures at unscheduled time points if deemed clinically necessary by the investigator.

Given lack of information regarding safety and tolerability of this combination regimen, the first 3 patients should be staggered (second patient should not be able to begin treatment until 3 weeks after the first patient has begun the treatment, i.e. completed cycle 1, similarly third patient should not begin treatment until second patient has completed cycle 1). Moreover, patients should be observed for 3 weeks for DLTs

Furthermore, additional evaluations/testing may be deemed necessary by the Sponsor and/or Merck for reasons related to participant safety. In some cases, such evaluation/testing may be potentially sensitive in nature (e.g., HIV, Hepatitis C, etc.), and thus local regulations may require that additional informed consent be obtained from the participant. In these cases, such evaluations/testing will be performed in accordance with those regulations.

7.1.1 Administrative Procedures

7.1.1.1 Informed Consent

The Investigator must obtain documented consent from each potential participant prior to participating in a clinical trial.

7.1.1.1 General Informed Consent

Consent must be documented by the participant's dated signature or by the participant's legally acceptable representative's dated signature on a consent form along with the dated signature of the person conducting the consent discussion.

A copy of the signed and dated consent form should be given to the participant before participation in the trial.

The initial informed consent form, any subsequent revised written informed consent form and any written information provided to the participant must receive the IRB/ERC's approval/favorable opinion in advance of use. The participant or his/her legally acceptable representative should be informed in a timely manner if new information becomes available that may be relevant to the participant's willingness to continue participation in the trial. The communication of this information will be provided and documented via a revised consent form or addendum to the original consent form that captures the participant's dated signature or by the participant's legally acceptable representative's dated signature.

Specifics about a trial and the trial population will be added to the consent form template at the protocol level.

HCC 18-087

The informed consent will adhere to IRB/ERC requirements, applicable laws and regulations and Sponsor requirements.

7.1.1.2 Inclusion/Exclusion Criteria

All inclusion and exclusion criteria will be reviewed by the investigator or qualified designee to ensure that the participant qualifies for the trial.

7.1.1.3 Medical History

A medical history will be obtained by the investigator or qualified designee. Medical history will include all active conditions, and any condition diagnosed within the prior 10 years that are considered to be clinically significant by the Investigator. Details regarding the disease for which the participant has enrolled in this study will be recorded separately and not listed as medical history.

7.1.1.4 Prior and Concomitant Medications Review

7.1.1.4.1 Prior Medications

The investigator or qualified designee will review prior medication use, including any protocol-specified washout requirement, and record prior medication taken by the participant within 28 days before starting the trial. Treatment for the disease for which the participant has enrolled in this study will be recorded separately and not listed as a prior medication.

7.1.1.4.2 Concomitant Medications

The investigator or qualified designee will record medication, if any, taken by the participant during the trial. All medications related to reportable SAEs and ECIs should be recorded as defined in Section 7.2.

7.1.1.5 Disease Details and Treatments

7.1.1.5.1 Disease Details

The investigator or qualified designee will obtain prior and current details regarding disease status.

7.1.1.5.2 Prior Treatment Details

The investigator or qualified designee will review all prior cancer treatments including systemic treatments, radiation and surgeries.

7.1.1.5.3 Subsequent Anti-Cancer Therapy Status

The investigator or qualified designee will review all new anti-neoplastic therapy initiated after the last dose of trial treatment. If a participant initiates a new anti-cancer therapy within 30 days after the last dose of trial treatment, the 30-day Safety Follow-up visit must occur before the first dose of the new therapy. Once new anti-cancer therapy has been initiated the participant will move into survival follow-up.

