5.5.2 Prohibited Concomitant Medications

Participants are prohibited from receiving the following therapies during the Screening and Treatment Phase of this trial:

- Antineoplastic systemic chemotherapy or biological therapy
- Immunotherapy not specified in this protocol
- Chemotherapy not specified in this protocol
- Investigational agents other than pembrolizumab
- Radiation therapy
 - Note: Radiation therapy to a symptomatic solitary lesion or to the brain may be allowed at the investigator's discretion.
- Live vaccines within 30 days prior to the first dose of study treatment and while participating in the study. Examples of live vaccines include, but are not limited to, the following: measles, mumps, rubella, varicella/zoster, yellow fever, rabies, BCG, and typhoid vaccine. Seasonal influenza vaccines for injection are generally killed virus vaccines and are allowed; however, intranasal influenza vaccines (e.g., FluMist®) are live attenuated vaccines and are not allowed.
- Systemic glucocorticoids for any purpose other than to modulate symptoms from an event of clinical interest of suspected immunologic etiology. The use of physiologic doses of corticosteroids may be approved after consultation with the Sponsor.

Participants who, in the assessment by the investigator, require the use of any of the aforementioned treatments for clinical management should be removed from the study. All treatments that the Investigator considers necessary for a participant's welfare may be

administered at the discretion of the Investigator in keeping with the community standards of medical care.

Medications or vaccinations specifically prohibited in the exclusion criteria are not allowed during the ongoing study. If there is a clinical indication for any medication or vaccination specifically prohibited during the study, discontinuation from study therapy or vaccination may be required. The final decision on any supportive therapy or vaccination rests with the investigator and/or the participant's primary physician. However, the decision to continue the participant on study treatment requires the mutual agreement of the investigator, the Sponsor, and the participant.

There are no prohibited therapies during the Post-Treatment Follow-up Phase.

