7.1.2.6.2 End of Treatment and Follow-up Tumor Imaging

In participants who discontinue study treatment, tumor imaging should be performed at the time of treatment discontinuation (±4-week window). If previous imaging was obtained within 4 weeks prior to the date of discontinuation, then imaging at treatment discontinuation is not mandatory. In participants who discontinue study treatment due to documented disease progression and the Investigator elects not to implement iRECIST, this is the final required tumor imaging.

In participants who discontinue study treatment without documented disease progression, every effort should be made to continue monitoring their disease status by tumor imaging using the same imaging schedule used while on treatment (every 12 weeks in Year 1 or every 12 weeks after Year 1) to monitor disease status until the start of a new anticancer treatment, disease progression, pregnancy, death, withdrawal of consent, or the end of the study, whichever occurs first.

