7.1.5.3.2 Follow-up Visits

Version Dated 5-20-2021

Participants who discontinue study treatment for a reason other than disease progression will move into the Follow-Up Phase and should be assessed every 12 weeks (84 \pm 14 days) by radiologic imaging to monitor disease status. Every effort should be made to collect information regarding disease status until the start of new anti-cancer therapy, disease progression, death, end of the study. Information regarding post-study anti-cancer treatment will be collected if new treatment is initiated.

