7.1.5.3.3 Survival Follow-up

Participants who experience confirmed disease progression or start a new anticancer therapy, will move into the Survival Follow-Up Phase and will be obtained from the medical record or contacted by telephone every 12 weeks (+/- 4 weeks) to assess for survival status until death, withdrawal of consent, or the end of the trial, whichever occurs first.

7.2 **Assessing and Recording Adverse Events**

An adverse event is defined as any untoward medical occurrence in a patient or clinical investigation participant administered a pharmaceutical product and which does not necessarily have to have a causal relationship with this treatment. An adverse event can therefore be any unfavorable and unintended sign (including an abnormal laboratory finding, for example), symptom, or disease temporally associated with the use of a medicinal product or protocol-specified procedure, whether or not considered related to the medicinal product or protocol-specified procedure. Any worsening (i.e., any clinically significant adverse change in frequency and/or intensity) of a preexisting condition that is temporally associated with the use of the Merck's product, is also an adverse event.

Changes resulting from normal growth and development that do not vary significantly in frequency or severity from expected levels are not to be considered adverse events. Examples of this may include, but are not limited to, teething, typical crying in infants and children and onset of menses or menopause occurring at a physiologically appropriate time.

Merck product includes any pharmaceutical product, biological product, device, diagnostic agent or protocol-specified procedure, whether investigational (including placebo or active comparator medication) or marketed, manufactured by, licensed by, provided by or distributed by Merck for human use.

Adverse events may occur during the course of the use of Merck product in clinical trials, or as prescribed in clinical practice, from overdose (whether accidental or intentional), from abuse and from withdrawal.

All AEs, SAEs and other reportable safety events that occur after the consent form is signed but before treatment allocation/randomization must be reported by the investigator if the participant is receiving placebo run-in or other run-in treatment, if the event cause the

59

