8.2 Statistical Analysis Plan

Proposed Data Analysis Primary Objectives

Objective response rate and progression-free based on RECIST 1.1 criteria (RC) will be estimated with 90% confidence intervals. The objective response rate (ORR) will be estimated by the proportion of subjects with the best response of complete response (CR), or partial response (PR) by RC, with corresponding exact 90% confidence limits being reported.

Proposed Data Analysis Secondary Analysis

The progression-free survival (PFS) will be measured from the initial date of the study treatment to the date of documented tumor progression using RC, or the date of death in the absence of tumor progression. PFS will be estimated by the Kaplan-Meier method with Greenwood 90% confidence intervals

Within-patient changes in CD8+ cells will be measured in tumor tissue and in peritoneal fluid at weeks 1,8, and 12. Mixed linear models will be used to estimate changes from baseline.

An assessment of the association among immune parameters, and ORR will be conducted. Endpoints for analysis include (CTL, NK- and Th1 cells) in the peritoneal fluid and resected residual tumor mass The panel of immune parameters will be tested for association with objective response with the Jonckheere-Terpstra test for trend by ordering response 1-4 for PD, SD, PR and CR, respectively. Significant association will be adjusted for initial tumor grade, and the interval between initial diagnosis of OC and protocol accrual. To guard against false positive results, the estimated false discovery rate will be calculated by the method of Benjamini and Hochberg (J. R. Statist. Soc. B Vol 57, No 1, 289-300, 1995).

HCC 18-087 Version Dated 5-20-2021

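### Disease follow-up ends when a new anticancer therapy starts, some text points the other way, and PFS has no rule for the switch, so its value depends on an unwritten choice

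*Combined protocol and SAP*

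**What the plan says.** **Text that ends disease follow-up at a new therapy** (combined protocol and SAP)

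- Section 7.1.1.5.3: "Once new anti-cancer therapy has been initiated the participant will move into survival follow-up".
- Section 7.1.2.6.2, for patients who stop study treatment without progression: imaging continues "to monitor disease status until the start of a new anticancer treatment, disease progression, pregnancy, death, withdrawal of consent" or the end of the study.
- Section 7.1.5.3.2 asks sites to "collect information regarding disease status until the start of new anti-cancer therapy, disease progression, death, end of the study".
- Section 7.1.5.3.3: "Participants who experience confirmed disease progression or start a new anticancer therapy, will move into the Survival Follow-Up Phase". Contact there is by medical record or telephone every 12 weeks, "to assess for survival status until death, withdrawal of consent, or the end of the trial, whichever occurs first".

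**Text that points the other way**

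- Section 7.1.2.6.1 (tumor imaging during the study) has scans continue until the investigator identifies progression and does not mention new therapy.
- The flow chart in section 6.1 marks CT imaging in the survival follow-up column.
- Section 3.1 follows patients for 3 years or until recurrence, to obtain time to progression (TTP), the ratio of the progression-free interval (PFI) to the patient's initial one, and 3-year PFS.

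**Analysis text**

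Section 8.2 runs PFS from first study treatment to documented RECIST 1.1 progression, "or the date of death in the absence of tumor progression", estimated by Kaplan-Meier with 90% intervals. It states no censoring rule of any kind and no rule for new anticancer therapy.

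**The concern.** Switching before RECIST progression is foreseeable. Section 5.6 stops study treatment for side effects, catheter infection, bowel obstruction or noncompliance. Section 5.2.2 removes patients with persisting further creatinine rises. Section 5.5.2 adds: "There are no prohibited therapies during the Post-Treatment Follow-up Phase". Section 7.1.1.5.3 itself plans for new therapy within 30 days of the last dose.

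Under the sections that end disease follow-up, such a patient's later progression is not collected. Section 8.2 does not say what happens to her in the PFS curve. The analyst must choose, in an open-label single-arm trial where the choice could be made after the data are seen. The possible choices move the estimate in different directions.

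For these patients the progression date needed for TTP and the PFI ratio is also lost.

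**Working it through.** **No plan figure to reproduce.** The documents give no assumed PFS median, event count, power or switching rate. What follows is illustration on assumed inputs.

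**Step 1: literal reading, switch unrelated to impending progression.**

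Assumptions:
- Time to progression is exponential with median 12 months, so λ = ln 2/12 = 0.0578 per month.
- Progression to death is exponential with median 24 months, so μ = ln 2/24 = 0.0289 per month.
- A fraction f of those progression-free at month 7 switch then. Month 7 is about the time of the planned week-31 catheter removal.
- A switcher's recorded event is death.

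Progression-free at month 7: exp(−7λ) = 0.667. With u = t − 7 and λ = 2μ, a switcher is still alive at t with probability 2e^(−μu) − e^(−λu). For t > 7 the recorded curve is therefore

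S(t) = 0.667 × [(1 − f)e^(−λu) + f(2e^(−μu) − e^(−λu))].

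*36 months (u = 29).* e^(−λu) = 0.187 and e^(−μu) = 0.433, so the switcher term is 2 × 0.433 − 0.187 = 0.678.
- f = 0: 0.667 × 0.187 = 12.5%
- f = 0.10: 0.667 × (0.9 × 0.187 + 0.1 × 0.678) = 15.8%
- f = 0.20: 0.667 × (0.8 × 0.187 + 0.2 × 0.678) = 19.1%

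*Median.* Put x = e^(−μu) and solve (1 − 2f)x² + 2fx = 0.5/0.667 = 0.749.
- f = 0.10: x = 0.851, u = 5.6, median 12.6 months
- f = 0.20: x = 0.833, u = 6.3, median 13.3 months

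Among 45 patients these fractions are 45 × 0.667 × 0.10 = 3 and 45 × 0.667 × 0.20 = 6 switchers.

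**Step 2: switch that foreshadows progression, three handlings.**

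Same two medians. Here a fraction of all patients leave imaging at a uniform 50–100% of their own time to progression (simulation, 400,000 patients per scenario).

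| Share switching | Handling | Median PFS, months | 36-month PFS |
|---|---|---|---|
| 10% | True value | 12.0 | 12.4% |
| 10% | Run to death (literal) | 13.6 | 17.0% |
| 10% | Censor at switch | 13.1 | 14.5% |
| 10% | Switch is an event | 11.6 | 11.8% |
| 20% | True value | 12.0 | 12.6% |
| 20% | Run to death (literal) | 15.6 | 21.6% |
| 20% | Censor at switch | 14.6 | 17.2% |
| 20% | Switch is an event | 11.3 | 11.3% |

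The exact 36-month value is 12.5%; the true-value rows differ from it by simulation error. The literal reading lengthens PFS most. Censoring at the switch keeps much of the excess when the switch is informative; in Step 1, where it is not, censoring would be unbiased. Counting the switch as an event shortens PFS.

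**The case against.** **The sections conflict, so follow-up may not stop.** This stands in part. The three contrary texts are real and need reconciling. None is specific to patients who start a new therapy, whereas the four sections that end follow-up name that event. The CT mark may cover only patients who have not progressed: the flow chart has no separate column for the follow-up phase, and its imaging footnote describes no scans after a switch.

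**Section 8.2 is silent, and silence is compatible with censoring at the last scan.** This stands. The text does not say that a switcher is carried event-free to her last survival contact, and section 7.1.5.3.2 already collects post-study treatment, so such censoring could be applied. Step 2 shows that it would not be neutral if the switch is informative, and it cannot recover a progression date that was never recorded.

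**The size is assumed.** This stands. With 45 patients fully followed and a true median of 12 months, the sample median ranges from 8.3 to 16.8 months (5th to 95th percentile), wider than any shift shown here. That does not remove a bias, but it keeps the point in proportion.

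**Stronger readings that a reader might infer, and that the documents do not support:**
- *The bias is always upward.* True only of the literal reading.
- *PFS is judged against history, so the error feeds a decision.* Sections 3.1 and 8.1 set the historical comparison for response rate. Section 8.2 only estimates PFS, with no benchmark or decision rule. Only the PFI ratio has a stated comparator, the patient's own earlier interval.
- *TTP and the PFI ratio cannot be obtained.* Only switchers lose the date, and TTP with censoring remains estimable.

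**Conclusion.** The concern holds in a bounded form. Four sections end disease follow-up at a new therapy without requiring progression, three texts point the other way, and the PFS definition has no rule for the switch. This is more than missing detail, because the stated cut-off discards progression dates that the section 3.1 endpoints need.

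Read literally, PFS is lengthened. On the Step 1 assumptions the median moves from 12 to 12.6 months with 10% switching and to about 13.3 with 20%; 3-year PFS moves from 12.5% to 16% and 19%. These figures rest on exponential times, the two assumed medians and the assumed switching shares. With no switchers before progression there is no effect.

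PFS is secondary. A reader might take this as doubt about the primary result; it is not, since the week-13 response rate and the Simon rule do not use these data. The point should be settled before analysis.

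**What to change.** 1. Reconcile sections 3.1, 6.1 and 7.1.2.6.1 with 7.1.1.5.3, 7.1.2.6.2, 7.1.5.3.2 and 7.1.5.3.3, so that one statement says what disease information is collected after a new therapy starts.
2. In 7.1.1.5.3 and 7.1.5.3.3, record the date of first progression from routine scans or the medical record at the existing 12-weekly contacts, including after a switch.
3. In 8.2, name one primary PFS handling in advance and give the other as a sensitivity analysis: (a) progression or death regardless of new therapy; (b) censoring at the last adequate scan before the switch.
4. Where no later progression date can be obtained, censor at the last adequate disease assessment. Do not carry the patient event-free to death or last survival contact.

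**Cost.** One case report form field at a contact already planned, a few sentences in section 8.2 and the protocol, and no change to treatment, visits or sample size. Post-switch dates will rest on routine-care imaging and may be incompletely ascertained. Handling (a) includes any effect of the next therapy, and handling (b) keeps the upward bias if switching is informative, which is why both should be shown. Reported PFS may be slightly less favourable.

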7.1.2 Clinical Procedures/Assessments

7.1.2.1 Adverse Event (AE) Monitoring

The investigator or qualified designee will assess each participant to evaluate for potential new or worsening AEs as specified in the Trial Flow Chart and more frequently if clinically indicated. Adverse experiences will be graded and recorded throughout the study and during the follow-up period according to NCI CTCAE Version 5.0 (see Appendix 2). Toxicities will be characterized in terms regarding seriousness, causality, toxicity grading, and action taken with regard to trial treatment.

Please refer to section 7.2 for detailed information regarding the assessment and recording of AEs.

7.1.2.2 Full Physical Exam

The investigator or qualified designee will perform a complete physical exam during the screening period. Clinically significant abnormal findings should be recorded as medical history. A full physical exam should be performed during screening,

7.1.2.3 Directed Physical Exam

For cycles that do not require a full physical exam per the Trial Flow Chart, the investigator or qualified designee will perform a directed physical exam as clinically indicated prior to trial treatment administration.

7.1.2.4 Vital Signs

The investigator or qualified designee will take vital signs at screening, prior to the administration of each dose of trial treatment and at treatment discontinuation as specified in the Trial Flow Chart (Section 6.0). Vital signs should include temperature, pulse, respiratory rate, weight and blood pressure. Height will be measured at screening only.

7.1.2.5 Eastern Cooperative Oncology Group (ECOG) Performance Scale

The investigator or qualified designee will assess ECOG status (see Appendix 1) at screening, prior to the administration of each dose of trial treatment and discontinuation of trial treatment as specified in the Trial Flow Chart.

